4.6.1 Rationale for the Part 1 Starting Dose of Modakafusp Alfa

In view of the marked decrease in modakafusp alfa plasma concentrations observed in repeated dosing in the nonhuman primate toxicology studies, a MABEL calculation was used to provide a framework for determining the FIH starting dose.

The calculation of the MABEL was based on projection of CD38 occupancy that would be maximally achievable at peak concentrations of modakafusp alfa following intravenous (IV) dosing (Saber et al. 2016). Although modakafusp alfa was initially (prior to Amendment 5) administered over a 4-hour ramped infusion (Section 8.1), in the absence of clinical PK data on modakafusp alfa, the calculation conservatively assumed dilution of the entire dose instantaneously in total plasma volume (2.8 L for a 70 kg patient). As such, a dose of 0.001 mg/kg (70 µg for a 70 kg patient) would be expected to achieve a maximum serum concentration of modakafusp alfa of no greater than 25 ng/mL (134 pM based on a molecular weight of 186 KDa). On the basis of the in vitro estimate of the CD38 target K_D of 168 pM (determined by a surface plasmon resonance assay), this translates to a projected receptor occupancy of <44% at the proposed starting dose of 0.001 mg/kg.

4.6.2 Rationale for Part 3

The rationale for conducting Part 3 of Study TAK-573-1501 is based on the totality of the data from Part 1 (dose escalation) and Part 2 (dose expansion) of Study TAK-573-1501.

Part 1 of Study TAK-573-1501 involved extensive dose exploration with 10 modakafusp alfa dose levels ranging from 0.001 mg/kg to 6.0 mg/kg on 4 different dosing schedules. The optimal schedule for modakafusp alfa was determined to be every 4 weeks (Q4W) based on the recovery time of hematological toxicities. The maximum tolerated dose (MTD) at this schedule was established as 3 mg/kg as 6 mg/kg exceeded the MTD with 2 dose-limiting toxicities (DLTs) (Grade 3 IRR and a greater than 2-week delay in start of cycle 2 due to thrombocytopenia and neutropenia). No DLTs were seen at 3 mg/kg. Preliminary efficacy activity was also seen in dose-escalation with 1 PR and 2 minimal responses (MRs) in 5 patients at 1.5 mg/kg on the Q4W schedule and 1 PR and 1 CR (patient ongoing at Cycle 21) in 7 patients at 3 mg/kg on the Q4W schedule.

Part 2 of Study TAK-573-1501 included a dose-expansion cohort of 25 patients treated at 1.5 mg/kg Q4W. A response rate of 44% was seen. The median duration of response has not yet been reached.

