9.4.1 Discontinuation of Treatment with Study Drug and Patient Replacement

Study drug must be permanently discontinued for patients meeting any of the following criteria:

• Patient experiences an AE or other medical condition that indicates to the investigator that continued participation is not in the best interest of the patient.

Treatment with study drug may also be discontinued for any of the following reasons:

- AE.
- Complete 1 year of treatment (unless exception is granted by the sponsor) in Parts 1 and 2 only.
- Protocol deviation (after discussion with sponsor).
- Progressive disease (if the investigator considers that treatment after PD is in the patient's best interest, it can be approved after consultation with the sponsor).
- Symptomatic deterioration.
- Unsatisfactory therapeutic response.

- Study terminated by sponsor.
- Withdrawal by subject.
- Female patient has confirmed pregnancy.
- Lost to follow-up.
- Other.

Once study drug has been discontinued, all study procedures outlined for the EOT visit will be completed as specified in the SOE (Appendix A). The primary reason for study drug discontinuation will be recorded on the eCRF.

In Part 1, patients who miss 1 or more modakafusp alfa infusions during Cycle 1 for reasons other than a DLT will be replaced. In Part 2 and Part 3, patients who receive 1 or more infusions of study drug will not be replaced.

Note that some patients may discontinue study drug for reasons other than PD before completing the full treatment course; these patients will remain in the study for posttreatment assessments as outlined in the SOE (Appendix A) until PD or withdrawal of consent.

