7.8 Efficacy Analysis

7.8.1 Part 1 and Part 2 Efficacy Analysis

Response evaluations after the start of subsequent anti-cancer therapy will not be considered in the calculation of efficacy endpoints, while the response evaluation after the treatment discontinuation will be considered in the calculation of efficacy endpoints. Please refer to Section 7.9.2 Part 3 Efficacy Analysis for details. When appropriate, data from patients in the

expansion cohorts will be summarized together with data from patients in the dose escalation phase.

Objective Response Rate (ORR)

The ORR is defined as the proportion of patients who achieved a confirmed PR or better during the study per investigator assessment as defined by IMWG Uniform Response Criteria. The ORR will be summarized by frequencies, percentages, and the exact two-sided 95% CIs based on the safety analysis set.

Clinical Benefit Rate (CBR)

The CBR includes patients with a confirmed response of sCR, CR, VGPR, PR, or MR during the study per investigator assessment as defined by IMWG Uniform Response Criteria. The CBR will be summarized by frequencies, percentages, and the exact two-sided 95% CIs based on the safety analysis set.

Disease Control Rate (DCR)

The DCR includes patients with a confirmed response sCR, CR, VGPR, PR, MR, or SD during the study per investigator assessment as defined by IMWG Uniform Response Criteria. The DCR will be summarized by frequencies, percentages, and the exact two-sided 95% CIs based on the safety analysis set.

Duration of Response (DOR)

The DOR will be calculated for those patients with a confirmed PR or better in the safety analysis set. The DOR is defined as the time from the first documentation of a confirmed response until progressive disease or death, whichever comes first. If there is no progressive disease or death observed, it will be censored at the last adequate response assessment. Please refer to Table 1 for the detailed censoring rules.

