In addition, time to the best response (the time from the first dose to the date of the first documentation of the best confirmed response [PR or better]) will be analyzed by using the same approach.

Overall Survival (OS)

Overall survival is defined as the time from the date of first dose to the date of death from any cause. Patients without documentation of death at the time of analysis will be censored at the date last known to be alive.

OS (months) = (date of death or censor – date of first dose + 1)/30.4375

The analysis of OS will be based on safety analysis set. The Kaplan-Meier method will be used to analyze the distribution of OS. Kaplan-Meier survival curves, the 25th, 50th (median), and 75th percentiles, along with the associated 2-sided 95% CIs based on Brookmeyer and Crowley method, and Kaplan-Meier estimates with 95% CIs at 6 and 12 months (or later time points if

data permits) will be presented. The number of patients with events and the number of patients censored will be summarized.

Best Overall Response

Best overall response is defined as the best response recorded after the first dose of study drug until subsequent anti-cancer therapy.

Confirmation of Response: All response categories except SD (sCR, CR, VGPR, PR, PD) require 2 consecutive adequate assessments made at any time before the initiation of subsequent anti-cancer therapy. There is no requirement on the time interval between the two visits.

Consecutive visits are needed for response confirmation, except if there is one or two “not evaluable” (NE) or “not done” (ND) assessments in between.

Either one or two consecutive occurrences of “ND” or “NE” between responses can be skipped when confirming a response such as:

PR -> NE -> PR: PR is considered to be confirmed in this case.

CR -> ND -> CR: CR is considered to be confirmed in this case.

Confirmation of PD:

1. If only one PD is recorded as the last available assessment prior to the subsequent anti-cancer therapy, it can be counted as a confirmed PD. It will be considered as an event for DOR, TTP, PFS analyses.

BL → SD → PD → Subsequent anti-cancer therapy/End – It is a confirmed PD

2. If only one PD value is recorded in the middle of responses better than PD as below, it will not be counted as a confirmed PD. It will not be considered as an event for DOR, TTP, PFS analyses.

BL → SD → PD → SD → SD → Subsequent anti-cancer therapy/End – It is not a confirmed PD.

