7.8.2 Part 3 Efficacy Analysis

7.8.2.1 Primary Efficacy Analysis

ORR, defined as the percentage of patients with a confirmed PR or better according to the IMWG Response Criteria. ORR based on IRC assessment will be analyzed as the primary endpoint. The primary analysis of ORR will be based on the full analysis set.

At the interim futility analyses, response status will be determined by a computer algorithm based on the IMWG Response Criteria. The algorithm will be specified in a separate document prior to the database lock. The algorithm based response will also be displayed at the time of primary analysis. A summary table of IRC-assessed, investigator-assessed, and algorithm-based best response with confirmation will be provided to assess the concordance rate at the time of primary analysis.

ORR at primary analysis will be analyzed based on the confirmed responses. Only the assessments from the start of treatment up to the earlier of confirmed disease progression or the start of subsequent anti-cancer therapy will be considered. Only subsequent systemic anti-cancer drugs taken are considered as anti-cancer therapy (radiotherapy and surgeries are not considered as systemic anti-cancer therapy for the purpose of this analysis). However, assessment after the treatment discontinuation will be considered. Subjects with only assessments of Not Evaluable or missing response will be treated as non-responders, i.e. they will be included in the denominator when calculating the percentage.

To confirm a response or progression, please refer to the details in Section 7.9.1 Best Overall Response.

The number and percentage of patients with BOR in the following response categories will be summarized by dose level: sCR, CR, VGPR, PR, MR, SD, PD, and NE/ND. The number and

CONFIDENTIAL

percentage of patients with ORR (sCR+CR+VGPR+PR) will be presented with the corresponding 2-sided 95% exact CI. A list of IRC-assessed response at each visit will be provided.

A waterfall plot showing the maximum percent reduction from baseline in serum M-protein, or urine M-protein, or difference between two types of serum FLC [Kappa light chain (Kappa LC) and Lambda light chain (Lambda LC)] for each subject will be generated by dose level. The plot will be color-coded for M-protein types and serum FLC.

Only the assessments from the start of treatment up to the start of a subsequent anti-cancer therapy will be considered.

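### SAP 7.8.1 does not clearly stop the Parts 1 and 2 response window at confirmed progression, so a response after progression could count in the Part 2 primary ORR

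*SAP*

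**What the plan says.** **Parts 1 and 2 (SAP 7.8.1).** The opening rule is "Response evaluations after the start of subsequent anti-cancer therapy will not be considered in the calculation of efficacy endpoints"; assessments after stopping study drug still count. The next sentence is "Please refer to Section 7.9.2 Part 3 Efficacy Analysis for details". ORR is then defined: "The ORR is defined as the proportion of patients who achieved a confirmed PR or better during the study per investigator assessment". Best overall response has its own window: "Best overall response is defined as the best response recorded after the first dose of study drug until subsequent anti-cancer therapy". The confirmation rule asks for two consecutive adequate assessments, again limited only by the start of new therapy.

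**Part 3 (SAP 7.8.2.1).** For ORR at the primary analysis, only assessments "up to the earlier of confirmed disease progression or the start of subsequent anti-cancer therapy will be considered". The waterfall plot in the same section is limited by subsequent therapy alone.

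**Treatment after progression.** Protocol 9.4.1 lists progression among reasons for which study drug may be stopped, and adds that "if the investigator considers that treatment after PD is in the" patient's best interest, it can be approved after the sponsor is consulted. That bullet names no part, although the one-year bullet in the same list is restricted to Parts 1 and 2. Protocol 2.0 (Duration of Treatment) and 6.3.1 place the same permission beside Part 3 text. Protocol 6.1 has Parts 1 and 2 dosing run until progression or another discontinuation criterion.

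**What rests on it.** ORR is the Part 2 primary endpoint, and a dose counts as clinically relevant with at least 11 responders in 25 (Protocol 13.3, SAP 6.0).

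**The concern.** A response rate normally stops accruing at progression, so that a patient is not counted first as a failure and then as a success. Part 3 of this SAP follows that convention expressly; the Parts 1 and 2 text does not. Where dosing can continue past progression, the difference has two consequences.

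- The Part 2 primary endpoint can gain responders from the wider window and cannot lose any, and it is judged against a fixed count in a small cohort.
- The endpoints stop fitting together for such a patient. PFS ends at the first confirmed progression, before the response begins. DOR starts at the response, and 7.8.1 does not say whether the earlier progression or a later one ends it.

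**Working it through.** **1. Does the cross-reference settle the window?** SAP v4 has no Section 7.9.2; Section 7.9 covers patient-reported outcomes. The title given in the pointer matches Section 7.8.2, and the change history in SAP 7.14 uses 7.9.2 for Part 3 material, so the target can be found. Once there, the cut at progression is in a sentence about ORR at the Part 3 primary analysis, and the same section uses a window without progression for the waterfall plot. The pointer gives a reason to apply the Part 3 window but does not clearly override the explicit definition of best overall response in 7.8.1.

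**2. Which patients are affected?** Using the confirmation rules in SAP 7.8.1, for a patient with no response before progression:

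| Sequence, still on drug, no new therapy | Progression confirmed? | Responder, 7.8.1 literal | Responder, 7.8.2.1 window |
|---|---|---|---|
| PD, PR, PR (PD not by imaging) | No: a lone PD followed by better results | Yes | Yes |
| PD, PD, PR, PR | Yes | Yes | No |
| Imaging PD, PR, PR | Yes: imaging PD can stand alone | Yes | No |

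Only the last two rows differ. The SAP formula is DOR = (date of progression, death or censoring − date of confirmed response + 1)/30.4375. Using the progression that precedes the response makes this zero or negative; using a later one gives a positive value that conflicts with the PFS event date.

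**3. Reproducing the plan's Part 2 figures.** Inputs from SAP 6.0 and 7.13 and Protocol 13.2.1 and 13.3: prior Beta(0.428, 1); stop at ≤3/10 or ≤5/15; success at ≥11/25.

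- P(success) = Σ Bin(a; 10, p) · Bin(b; 5, p) · P[Bin(10, p) ≥ 11 − a − b], summed over a ≥ 4 and a + b ≥ 6.
- At p = 0.30 this gives 7.6% (stated 7%); at p = 0.50, 69.8% (stated 70%). Without the futility looks the values are 9.8% and 78.8%, so the stated figures include them.
- Predictive probability of success is 0.134 at 3/10 and 0.124 at 5/15, both under 15% as stated.

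The plan's figures reproduce.

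**4. Effect of one patient.** 1/25 = 4 percentage points. The posterior after r responders is Beta(0.428 + r, 1 + 25 − r).

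- r = 11: Beta(11.428, 15), P(ORR > 30%) = 0.920, above the stated 90%.
- r = 10: Beta(10.428, 16), P(ORR > 30%) = 0.841, below it.

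**5. Sensitivity, on assumed shares.** The documents do not say how many non-responders would respond only after confirmed progression. Let that share be q, with a true pre-progression ORR of 30%. The counted rate is p = 0.30 + 0.70q, entered in the formula in step 3.

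| Assumed q | p | Chance of declaring success |
|---|---|---|
| 0% | 0.300 | 7.6% |
| 2% | 0.314 | 10.0% |
| 5% | 0.335 | 14.4% |
| 10% | 0.370 | 24.1% |

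This applies the raised rate at both futility looks as well. Responses after progression come late, so for a given q the figures lean high.

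**The case against.** The strongest reply is that Parts 1 and 2 already defer to the Part 3 window. The pointer follows directly on the rule about which evaluations count, names its target by title, and that target cuts at confirmed progression. This stands in part: a reader might infer that Parts 1 and 2 have no cut at progression at all, and the documents do not establish that. They show two windows joined by a stale number, with the reach of the Part 3 sentence left open.

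The confirmation wording adds little either way. Section 7.8.2.1 sends the reader to the same confirmation text (as Section 7.9.1, also stale), so its silence on progression coexists with a cut in Part 3.

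The affected group is also small. A lone PD followed by better results counts the same under either window. Under Protocol 6.3.1, scheduled PFS follow-up is for patients who stop for reasons other than progression. What remains is essentially patients dosed past a confirmed progression who first respond afterwards.

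Three stronger inferences are not supported:

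- **That the reported Part 2 result is inflated.** Protocol 4.6.2 states "A response rate of 44% was seen" in a cohort of 25, and 0.44 × 25 = 11, the threshold itself. Nothing indicates that any of those responses followed progression, and Part 3 was justified on the totality of Parts 1 and 2, not on this count alone.
- **That DOR is undefined.** A later progression or death can end it; what is unclear is how the earlier progression is treated.
- **That this is what makes Part 2 and Part 3 ORR non-comparable.** They already differ in assessor (investigator or IRC), laboratory (local or central) and eligibility.

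**Conclusion.** The point holds as an ambiguity in the window for the Part 2 primary endpoint. The literal text of 7.8.1 admits responses after confirmed progression, 7.8.2.1 excludes them for Part 3 ORR, and the pointer between them does not clearly decide the matter. The effect runs one way: the wider window can only raise ORR. One patient is worth 4 percentage points and separates a posterior of 0.920 from 0.841 at the decision threshold. This rests on Protocol 9.4.1 applying to Parts 1 and 2, as its wording allows, and on at least one patient following the narrow path in step 2. No such patient is documented, and the 2% to 10% shares in step 5 are illustrations. The stated operating characteristics are not in question.

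**What to change.** In SAP 7.8.1, state that best overall response, ORR and response confirmation use assessments "up to the earlier of confirmed disease progression or the start of subsequent anti-cancer therapy", as in 7.8.2.1. Correct the reference to 7.9.2 (in 7.8.1) to 7.8.2, and the reference to 7.9.1 (in 7.8.2.1) to 7.8.1.

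The protocol passages on treatment after progression (2.0 Duration of Treatment, 6.1, 6.3.1 and 9.4.1) should be reconciled so that it is clear what they mean for Parts 1 and 2. Which clinical rule should apply is for the sponsor to decide.

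The cost is a wording change and one derivation change. The Part 2 design figures are unaffected, and the Part 2 ORR can only stay the same or fall slightly.

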7.8.2 Part 3 Efficacy Analysis

7.8.2.1 Primary Efficacy Analysis

ORR, defined as the percentage of patients with a confirmed PR or better according to the IMWG Response Criteria. ORR based on IRC assessment will be analyzed as the primary endpoint. The primary analysis of ORR will be based on the full analysis set.

At the interim futility analyses, response status will be determined by a computer algorithm based on the IMWG Response Criteria. The algorithm will be specified in a separate document prior to the database lock. The algorithm based response will also be displayed at the time of primary analysis. A summary table of IRC-assessed, investigator-assessed, and algorithm-based best response with confirmation will be provided to assess the concordance rate at the time of primary analysis.

ORR at primary analysis will be analyzed based on the confirmed responses. Only the assessments from the start of treatment up to the earlier of confirmed disease progression or the start of subsequent anti-cancer therapy will be considered. Only subsequent systemic anti-cancer drugs taken are considered as anti-cancer therapy (radiotherapy and surgeries are not considered as systemic anti-cancer therapy for the purpose of this analysis). However, assessment after the treatment discontinuation will be considered. Subjects with only assessments of Not Evaluable or missing response will be treated as non-responders, i.e. they will be included in the denominator when calculating the percentage.

To confirm a response or progression, please refer to the details in Section 7.9.1 Best Overall Response.

The number and percentage of patients with BOR in the following response categories will be summarized by dose level: sCR, CR, VGPR, PR, MR, SD, PD, and NE/ND. The number and

CONFIDENTIAL

percentage of patients with ORR (sCR+CR+VGPR+PR) will be presented with the corresponding 2-sided 95% exact CI. A list of IRC-assessed response at each visit will be provided.

A waterfall plot showing the maximum percent reduction from baseline in serum M-protein, or urine M-protein, or difference between two types of serum FLC [Kappa light chain (Kappa LC) and Lambda light chain (Lambda LC)] for each subject will be generated by dose level. The plot will be color-coded for M-protein types and serum FLC.

Only the assessments from the start of treatment up to the start of a subsequent anti-cancer therapy will be considered.

The maximum percent reduction will be plotted in the following hierarchical order:

- [1] Plot the worse (higher) value of the maximum percent reduction from baseline in serum and urine M-protein if the patient has both serum and urine M-protein measurable;
- [2] Plot Serum M-protein maximum percent reduction from baseline if data is available;
- [3] If [2] is not feasible, plot Urine M-protein maximum percent reduction from baseline if data is available;
- [4] If both [2] and [3] are not feasible, plot maximum percent reduction from baseline for difference between two types of Serum FLC if data is available.

Difference between two types of serum free light chain (FLC)

The percent change from baseline for difference between two types of serum FLC is defined as:

$$(\text{post-baseline difference} - \text{baseline difference}) / \text{baseline difference} * 100\%$$

To calculate the difference, the “involved” and “non-involved” light chains must be determined at first based on the ratio of non-missing values for Serum Kappa LC protein and Serum Lambda LC protein at baseline.

The detailed algorithm is provided as below:

- If the baseline ratio of (Kappa LC/Lambda LC) > 1.65 , then Kappa LC is defined as involved FLC, and Lambda LC is defined as non-involved FLC. Then:
Difference between involved and uninvolved = Kappa LC-Lambda LC
- If the baseline ratio of (Kappa LC/Lambda LC) < 0.26 , then Lambda LC is defined as involved FLC, and Kappa LC is defined as non-involved FLC:
Difference between involved and uninvolved = Lambda LC-Kappa LC
- If the baseline ratio of (Kappa LC/Lambda LC) ≤ 1.65 and ≥ 0.26 , then “involved” and “non-involved” FLC cannot be determined (ratio is normal), and maximum percent reduction from baseline for difference between two types of Serum FLC won’t be available.

7.8.2.2 *Secondary Efficacy Analysis*

ORR based on Investigator Assessment

ORR based on investigator-assessed response will be analyzed as one of the secondary endpoints. It will be analyzed based on the confirmed responses by using the same analysis approach as for IRC-assessed ORR.

DOOR

DOOR is defined as the time from first documented evidence of confirmed PR or better until the earliest date of a confirmed PD per IMWG, or death among patients who achieve a response (i.e., confirmed PR or better). Responders without confirmed PD or death will be censored at the censoring time point for PFS as specified in Table 1.

DOOR will be analyzed at the time of primary ORR analysis, also at final analysis (study close out), based on the responses assessed by both IRC and investigator.

DOOR will be summarized using the Kaplan-Meier method by dose level for patients with a confirmed PR or better. Median DOOR, first and third quartiles, 3-month, 6-month, 9-month, 12-month DOOR rate (or later time points if data permits), and 95% CIs will be estimated using the Brookmeyer-Crowley method. A Kaplan-Meier plot of DOOR time will also be provided.

CBR

CBR is defined as the percentage of patients with a confirmed MR or better, according to the IMWG Response Criteria. CBR will be summarized in the same way as ORR. At the primary analysis, CBR based on both IRC and investigator assessment will be summarized. At interim analysis, investigator-assessed CBR will be summarized.

DCR

DCR is defined as the percentage of patients with a SD or confirmed MR or better, according to the IMWG Response Criteria. DCR will be summarized in the same way as ORR. At the primary analysis, DCR based on both IRC and investigator assessment will be summarized. At interim analysis, investigator-assessed DCR will be summarized.

For CBR and DCR, the number and percentage of patients with the CBR and DCR will be summarized by dose level. The corresponding exact 95% CI for CBR and DCR will also be provided. Patients with unknown or missing responses will be included in the denominator when calculating percentages of response.

Duration of Clinical Benefit

Duration of clinical benefit is defined as the time from first documented evidence of confirmed MR or better until the earliest date of a confirmed PD per IMWG, or death among patients who achieve a confirmed MR or better. Patients without confirmed PD or death will be censored at the censoring time point for PFS as specified in Table 1.

Duration of clinical benefit will be analyzed at the time of primary ORR analysis, also at final analysis (study close out), based on responses assessed by both IRC and investigator.

Duration of clinical benefit will be summarized using the Kaplan-Meier method by dose level for patients with a confirmed MR or better. Median duration of clinical benefit, first and third quartiles and 95% CI, will be estimated using the Brookmeyer-Crowley method.

Duration of Disease Control

Duration of disease control is defined as the time from first documented evidence of SD or better until the earliest date of a confirmed PD per IMWG, or death among patients who achieve a SD or better. Patients without confirmed PD or death will be censored at the censoring time point for PFS as specified in Table 1.

Duration of disease control will be analyzed at the time of primary ORR analysis, also at final analysis (study close out), based on responses assessed by both IRC and investigator.

Duration of disease control will be summarized using the Kaplan-Meier method by dose level for patients with a SD or confirmed MR or better. Median duration of disease control, first and third quartiles and 95% CI, will be estimated using the Brookmeyer-Crowley method.

PFS

PFS is defined as the time from the date of first dose until the earliest date of confirmed PD per IMWG, or death due to any cause. PFS will be analyzed at the time of primary analysis of ORR, also at final analysis (study close out), based on responses assessed by both IRC and investigator.

A summary of the assignments for progression and censoring dates for PFS are specified in Table 1 below.

Table 1 Assignments for Progression and Censoring Date for PFS Analysis

Scenarios	Event date/censoring date	Event status
No (or inadequate) baseline tumor assessments ¹	Date of the first dose	Censored
No post-baseline assessments	Date of the first dose	Censored
Confirmed progression documented without extended loss-to-follow-up time (two or more missed cycles) ⁴	Date of assessment of the earliest date of the confirmed progression	Event
No confirmed progression or death	Date of last adequate assessment of response ²	Censored
Subsequent anti-cancer therapy started (before documented confirmed progression or death) ³	Date of last adequate assessment of response ² (prior to the initiation of the subsequent anti-cancer therapy)	Censored
Death without extended loss-to-follow-up time	Death date	Event
Death or progression after an extended loss-to-follow-up time (two or more missed cycles) ⁴	Date of last adequate assessment of response ² (prior to missed assessments)	Censored

1. Adequate baseline assessment is defined as at baseline, a patient has at least one of the following measurements:
 - a. Serum M-protein $\geq 0.5\text{g/dL}$ ($\geq 500\text{ mg/dL}$) or
 - b. Urine M-protein $\geq 200\text{ mg/24 hours}$ or
 - c. Serum FLC assay: Involved FLC level $\geq 10\text{ mg/dL}$ ($\geq 100\text{ mg/L}$) and an abnormal serum FLC ratio (<0.26 or >1.65)
2. An adequate assessment is defined as an assessment where the IRC/investigator determined response is sCR, CR, VGPR, PR, MR, or SD prior to a subsequent anti-cancer therapy. An unconfirmed PD assessment is also considered as an adequate assessment.
3. If PD or death and the subsequent anti-cancer therapy occur on the same day, it is assumed that the progression or death was documented first (e.g., event status is an event, and the date of event is the date of progression or death). If the subsequent anti-cancer therapy is initiated prior to any adequate assessment, censoring date should be the date of the first dose.
4. Refer to Section 7.1.4 “Extended Loss-to-follow-up”

PFS will be summarized using the Kaplan-Meier method by dose level. Median PFS, first and third quartiles, 3-month, 6-month, 9-month, 12-month PFS rate (or later time points if data

permits), and 95% CIs will be estimated using the Brookmeyer-Crowley method. A Kaplan-Meier plot of PFS time will also be provided.

TTP

TTP is defined as the time from the date of the first dose until the earliest date of confirmed PD per IMWG.

TTP will be analyzed at the time of primary analysis of ORR, also at final analysis (study close out), based on responses assessed by both IRC and investigator.

A summary of the assignments for progression and censoring dates for TTP are specified in Table 2.

Table 2 Assignments for Progression and Censoring Date for TTP Analysis

Scenarios	Event date/censoring date	Event status
No (or inadequate) baseline tumor assessments ¹	Date of the first dose	Censored
No post-baseline assessments	Date of the first dose	Censored
Confirmed progression documented without extended loss-to-follow-up time (two or more missed cycles) ⁴	Date of assessment of the earliest date of the confirmed progression	Event
No confirmed progression or death	Date of last adequate assessment of response ²	Censored
Subsequent anti-cancer therapy started (before documented confirmed progression) ³	Date of last adequate assessment of response ² (on or prior to the initiation of the subsequent anti-cancer therapy)	Censored
Death	Date of last adequate assessment of response ² prior to death	Censored
Progression after an extended loss-to-follow-up time (two or more missed cycles) ⁴	Date of last adequate assessment of response ² (prior to missed assessments)	Censored

1. Adequate baseline assessment is defined as at baseline, a patient has at least one of the following measurements:

- a. Serum M-protein ≥ 0.5 g/dL (500 mg/dL) or
- b. Urine M-protein ≥ 200 mg/24 hours or

- c. Serum FLC assay: Involved FLC level ≥ 10 mg/dL (≥ 100 mg/L) and an abnormal serum FLC ratio (<0.26 or >1.65)
2. An adequate assessment is defined as an assessment where the IRC/investigator determined response is sCR, CR, VGPR, PR, MR, or SD prior to a subsequent therapy. An unconfirmed PD assessment is also considered as an adequate assessment.
3. If PD and the subsequent anti-cancer therapy occur on the same day, it is assumed that the progression was documented first (e.g., event status is an event, and the date of event is the date of progression). If the subsequent anti-cancer therapy is initiated prior to any adequate assessment, censoring date should be the date of the first dose.
4. Refer to Section 7.1.4 “Extended Loss-to-follow-up”

TTP will be summarized using the Kaplan-Meier method by dose level. Median TTP, first and third quartiles, 3-month, 6-month, 9-month, 12-month TTP rate (or later time points if data permits), and 95% CI will be estimated using the Brookmeyer-Crowley method. A Kaplan-Meier plot of TTP time will also be provided. Analysis of TTP will be based on both IRC and investigator-assessed responses.

OS

OS is defined as the time from the date of the first dose until death due to any cause. Patients who do not have a death record at the clinical cut-off date for the analysis will be censored at the last known alive date. The last known alive date will be determined by the latest collection/assessment date from among all data domains within the clinical database.

An OS analysis will be performed at the time of primary analysis of ORR, also at final analysis (study close out).

OS will be summarized using the Kaplan-Meier method by dose level. Median OS, first and third quartiles, and 95% CIs will be estimated using the Brookmeyer-Crowley method. A Kaplan-Meier plot and listing of OS time will also be provided. In addition, pending on maturity of data, the survival probability at 6, 12 and 18 months with 95% CI will be estimated using the Kaplan-Meier method.

MRD negativity at a sensitivity of 10^{-5}

MRD negativity at a sensitivity of 10^{-5} as a secondary endpoint is defined as patients who are MRD negative at a sensitivity of 10^{-5} in patients achieving suspected CR. Duration of MRD negativity (10^{-5}) is defined as the time from the first MRD negative status (10^{-5}) to the earliest date of the MRD positive status (10^{-5}), confirmed PD per IMWG or death.

For MRD negativity (10^{-5}) rate based on bone marrow testing, the number and percentage of patients who have achieved MRD negativity (10^{-5}) will be summarized by dose level. The corresponding exact 95% CI for MRD negativity (10^{-5}) rate will also be provided. The rate of maintaining MRD negativity (10^{-5}) will be reported in patients who achieve CR and MRD negativity (10^{-5}). Duration of MRD negativity (10^{-5}) will be analyzed using the Kaplan-Meier method in patients who have achieved MRD negativity (10^{-5}) when data permit; otherwise, a listing will be generated.

